7 SAFETY ASSESSMENTS

7.1 Known Potential Risks

- There is minimal risk associated with participating in this study for infants and parents.
- Children may be tired or a little fussy during or after the assessment or intervention study visits.
 - To mitigate this risk: The team includes experienced medical professionals and researchers who are trained to provide care in the NICCU, home, at CHLA, and at USC. All infants in the NICCU, home, at CHLA, or at USC will remain on any cardiac, respiratory, or oxygen monitors or supports. As part of the intervention, parents will be empowered to read their babies cues to anticipate the infants' level of fatigue and response by providing breaks. In addition, the interventions and assessments are no more stressful than standard care limiting the risk.
- For the parent/legal guardian participants the risks are minimal and include the possibility of feeling stressed about completing the interventions or assessment visits or parent could become emotionally distressed by talking about their NICCU experiences or current emotional status as it relates to providing the interventions. The risks are similar for all infants.
 - To mitigate the risk of parent stress, parent/legal guardian participants will be asked to do the best they can to complete the intervention, but they will not be pressured or made to feel bad if they did not complete as much intervention as was requested.
 - To mitigate the risk of parents becoming emotionally distressed, the assessment and intervention team will be provided with a

resource manual including signs of depression and anxiety. Study staff will refer any parent who has signs of mental health conditions to their primary care physician or if emergent care is needed to the Emergency Department. In the 2 previous studies using this protocol no parent has needed to be referred to the emergency department.

- For both infants and parents there is a health risk from being in contact with people living outside the family home.
 - We thoroughly clean the toys, equipment, and surfaces infants and parents come into contact with before and after each visit.
 - If it is recommended by CHLA or USC to discontinue in-person visits due to COVID, we can provide assessment and intervention via telehealth.
- For both infants and parents there is the risk of loss of confidentiality and privacy as a part of being in this study.
 - To minimize loss of confidentiality and privacy, all electronic video data is stored on the USC OneDrive with a secure server. Medical records, scorable assessments, demographics, and visit records will be entered into a REDCap Database on HIPAA Compliant servers housed at USC with hard copies used during visits stored in lock cabinets in a locked office accessible by trained study staff. All assessment sessions and intervention sessions are completed in the NICCU, family home, at CHLA, or in the USC research lab with a locking door. All videos and forms used in the study will only be identified by the subject ID number and the date of the visit.

7.2 Known Potential Benefits

- It is possible that participating parents/legal guardians will report enjoyment or learning about their infant's development from participating in the assessment visits. In addition it is possible that infant participants will benefit from being in the SMI intervention group. However, this is the purpose of this study and therefore is not known at this time.
- Infants who will be included in this study are all eligible for early intervention developmental support services in California. However, there is little data to suggest what is best practice in the timing, dose, or type of intervention provided. This study will start to address this gap in the literature.
- Parents/legal guardians or infant participants will be given \$20 per assessment visit (3 total) and a small toy to compensate them for their time and participation in the study. Compensation will be provided as cash or a gift card.
- If a family chooses for their study visits to be at CHLA or USC, the family will be provided with a parking voucher.

7.1 Specification of Safety Parameters

7.2 Methods and Timing for Assessing, Recording, and Analyzing Safety Parameters

Adverse events will be assessed and recorded at each assessment and intervention session.

7.3 Adverse Events and Serious Adverse Events

Adverse event (AE) is defined as any untoward medical occurrence associated with the use of an intervention in humans, whether or not considered intervention-related (21 CFR 312.32 (a)).

An adverse event (AE) or suspected adverse reaction is considered "serious" if, in the view of either the investigator or sponsor, it results in any of the following outcomes: death, a life-threatening adverse event, inpatient hospitalization or prolongation of existing hospitalization, a persistent or significant incapacity or substantial disruption of the ability to conduct normal life functions, or a congenital anomaly/birth defect. Important medical events that may not result in death, be life-threatening, or require hospitalization may be considered serious when, based upon appropriate medical judgment, they may jeopardize the participant and may require medical or surgical intervention to prevent one of the outcomes listed in this definition. Examples of such medical events include lacerations requiring medical care or a head injury due to a fall.

For adverse events (AEs) not included in the protocol defined grading system, the following guidelines will be used to describe severity.

- **Mild** – Events require minimal or no treatment and do not interfere with the participant's daily activities.
- **Moderate** – Events result in a low level of inconvenience or concern with the therapeutic measures. Moderate events may cause some interference with functioning or require medical care.
- **Severe** – Events interrupt a participant's usual daily activity and may require hospitalization.

All adverse events (AEs) must have their relationship to study intervention assessed by the clinician who examines and evaluates the participant based on temporal relationship and his/her clinical judgment. The degree of certainty about causality will be graded using the categories below. In a clinical trial, the study product must always be suspect.

- **Definitely Related** – There is clear evidence to suggest a causal relationship, and other possible contributing factors can be ruled out.

- **Probably Related** – There is evidence to suggest a causal relationship, and the influence of other factors is unlikely.
- **Potentially Related** – There is some evidence to suggest a causal relationship. However, other factors may have contributed to the event (e.g., the participant’s clinical condition, other concomitant events). Although an AE may rate only as “possibly related” soon after discovery, it can be flagged as requiring more information and later be upgraded to “probably related” or “definitely related”, as appropriate.
- **Unlikely to be related** – A clinical event, including an abnormal laboratory test result, whose temporal relationship to study intervention administration makes a causal relationship improbable (e.g., the event did not occur within a reasonable time after administration of the study intervention).
- **Not Related** – The AE is completely independent of study intervention administration, and/or evidence exists that the event is definitely related to another etiology. There must be an alternative, definitive etiology documented by the clinician.

Site medically responsible investigator will be responsible for determining whether an adverse event (AE) is expected or unexpected. An AE will be considered unexpected if the nature, severity, or frequency of the event is not consistent with the risk information previously described for the study intervention.

7.4 Reporting Procedures

All AEs including local and systemic reactions not meeting the criteria for SAEs will be captured on the appropriate case report form (CRF). Information to be collected includes event description, time of onset, clinician’s assessment of severity, relationship to study product (assessed only by those with the training and authority to make a diagnosis), and time of resolution/stabilization of the event. All AEs occurring while on study must be documented appropriately regardless of relationship. All AEs will be followed to adequate resolution.

Any medical condition that is present at the time that the participant is screened will be considered as baseline and not reported as an AE. However, if the study participant’s condition deteriorates at any time during the study, it will be recorded as an AE.

Changes in the severity of an AE will be documented to allow an assessment of the duration of the event at each level of severity to be performed. AEs characterized as intermittent require documentation of onset and duration of each episode.

7.5 Follow-up for Adverse Events

The PI will record all reportable events with start dates occurring any time after informed consent is obtained until 7 days (for non-serious AEs) or 30 days (for SAEs) after the last day of study participation. At each study visit, the investigator will inquire about the occurrence of AE/SAEs since the last visit. Events will be followed for outcome information until resolution or stabilization.

7.6 Safety Monitoring

The PI will be responsible for safety monitoring. All assessors and interventionists will ask the parent/legal guardian about adverse events at every study visit and the PI will report them to the IRB as stated above. The PI will regularly review the data collected, including adverse events, and will formally review the SMI intervention midway and at the end of enrollment of infants receiving the SMI intervention.

8 INTERVENTION DISCONTINUATION

Discontinuation from the SMI intervention does not mean discontinuation from the study, and remaining study procedures should be completed as indicated by the study protocol. If a clinically significant finding is identified (including, but not limited to changes from baseline) after enrollment, the investigator or qualified designee will determine if any change in participant management is needed. Any new clinically relevant finding will be reported as an adverse event (AE).

Participants are free to withdraw from participation in the study at any time upon request. An investigator may discontinue or withdraw a participant from the study for the following reasons:

- Significant study intervention non-compliance (Losing touch with the family / missing more than 3 visits)
- Infants who become medically unstable or requires ventilator support prohibiting participation in more than 1 assessment or 10 days of intervention will be dropped from the study.
- If any clinical adverse event (AE), or other medical condition or situation occurs such that continued participation in the study would not be in the best interest of the participant
- If the participant meets an exclusion criterion (either newly developed or not previously recognized) that precludes further study participation
- Participant unable to receive SMI therapist or parent delivered intervention for 10 consecutive days.

The reason for participant discontinuation or withdrawal from the study will be recorded in the participant tracking records. Subjects who sign the informed consent form and are randomized but do not receive the study intervention may be replaced. Subjects who sign the informed consent form, and are randomized and receive the study intervention, and subsequently withdraw, or are withdrawn or discontinued from the study, will not be replaced.

A participant will be considered lost to follow-up if he or she fails to return for 2 consecutive assessment visits or 3 intervention visits and is unable to be contacted by the study site staff.

The following actions must be taken if a participant fails to return to the clinic for a required study visit:

- The site will attempt to contact the participant and reschedule the missed visit within a week and counsel the participant on the importance of maintaining the assigned visit schedule and ascertain if the participant wishes to and/or should continue in the study.
- Before a participant is deemed lost to follow-up, the investigator or designee will make every effort to regain contact with the participant (where possible, 3 telephone calls and, if necessary, a certified letter to the participant's last known mailing address or local equivalent methods). These contact attempts should be documented in the participant's study file.
- Should the participant continue to be unreachable, he or she will be considered to have withdrawn from the study with a primary reason of lost to follow-up.

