4.4 Withdrawal Criteria

- Participants are free to withdraw from participation in the study at any time upon request. The reason for participant discontinuation or withdrawal from the study will be recorded in the participant tracking records in REDCap. Participants who sign the informed consent form, and receive the study intervention, and subsequently withdraw, or are withdrawn or discontinued from the study, will not be replaced.
- Significant study intervention non-adherence (Losing touch with the family / missing more than 5 visits without contacting the research team.)
- Infants who become medically unstable prohibiting participation in more than 1 assessment or 3 days of intervention will be dropped from the study.
- If any clinical adverse event (AE), or other medical condition (i.e. Acute Fractures, Cancer, etc) or situation occurs such that continued participation in the study would not be in the best interest of the participant or they will be unable to participate fully.
- Participant unable to be reached.

5 **STUDY INTERVENTIONS**

5.1 **Interventions, Administration, and Duration**

Standard care intervention provided to infants. Intervention will begin after an infant has met the following conditions: extubated and weaned to respiratory support that is ≤ 2 L per minute canula flow, not requiring vasopressors, and no diagnosis of status epilepticus for ≥ 24 hours. Infants will receive standard care in their respective NICCU and community. Typical service in the NICCU will include routine medical care, physical, occupational, or speech therapy assessments and referral to the infant's local Early Intervention program as deemed necessary by the medical team. All infants will be referred to the High-Risk Newborn Follow-Up Clinic per current clinical policy.

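### Sections 4.4 and 8 set conflicting limits for withdrawal from the study, and both let missed SMI end the assessments as well, so A2 and A3 can be lost from families who are still reachable

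*Combined protocol and SAP*

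**What the plan says.** Section 4.4 (Withdrawal Criteria) gives two limits relevant here. For non-adherence it is losing touch with the family or "missing more than 5 visits without contacting the research team". For instability: "Infants who become medically unstable prohibiting participation in more than 1 assessment or 3 days of intervention will be dropped from the study".

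Section 8 (Intervention Discontinuation) opens with a retention principle: "Discontinuation from the SMI intervention does not mean discontinuation from the study". It adds that the remaining procedures are to be carried out. It then continues: "An investigator may discontinue or withdraw a participant from the study for the following reasons". The list includes:

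- "Significant study intervention non-compliance (Losing touch with the family / missing more than 3 visits", with no condition about contact;
- infants who become unstable or need a ventilator, "prohibiting participation in more than 1 assessment or 10 days of intervention will be dropped from the study";
- "Participant unable to receive SMI therapist or parent delivered intervention for 10 consecutive days".

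Section 8 also defines loss to follow-up as a participant who "fails to return for 2 consecutive assessment visits or 3 intervention visits and is unable to be contacted by the study site staff". Such a participant counts as withdrawn.

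Other relevant text: 5.4 classes a dyad below 70% of planned sessions as non-adherent. H2a asks for 8 of 10 visits, H2b for 80% of sampled days, and H3a for the baseline and all three assessments. Section 9.1 names A3 as the primary endpoint. Section 9.5 reports the feasibility hypotheses descriptively and does not say how withdrawn dyads are counted. Both 4.4 and 8 say that dyads who have received SMI and then leave are not replaced.

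**The concern.** The same dyad can be kept or withdrawn depending on which section staff apply. Both sections also treat failure to take up the intervention as a reason to leave the study, which works against section 8's own opening sentence.

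Assessment completion (H3a) is a primary feasibility outcome. A3 supplies the Bayley-4 scores wanted for planning later trials. A2 and A3 carry the parenting stress measure, which section 6.2.2 says is collected to see whether the intervention burdens families. Families who stop attending SMI are the ones in whom that question most needs an answer, and the withdrawal rules allow staff to stop assessing them.

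**Working it through.** The plan gives no figure to reproduce: there is no power analysis and no expected attendance or dropout. The check compares the rules and works out when each would apply.

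**1. The limits side by side**

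| Rule | Section 4.4 | Section 8 |
|---|---|---|
| Missed visits | more than 5, no contact made | more than 3, no contact condition |
| Instability | 3 days of intervention | 10 days of intervention |
| Gap in SMI | none | 10 consecutive days |
| Unreachable | unable to be reached | 3 intervention visits, or 2 consecutive assessments |

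Both instability rules are worded as mandatory, although section 8's sits in a permissive list. An infant unstable for 4 to 9 days is dropped under 4.4 and does not reach section 8's limit.

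**2. Who is caught, with 10 planned sessions**

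- Section 5.4: 0.70 × 10 = 7, so non-adherent means 6 or fewer attended, that is 4 or more missed. This is exactly section 8's missed-visit group.
- H2a needs 8 attended. Everyone in that group has already failed H2a, so missed-visit withdrawal cannot turn an H2a success into a failure.
- Section 4.4's limit means 4 or fewer attended, and no contact.

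**3. When the limits are reached**

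Home visits fall at weeks 1, 3, 5, 8, 11, 15, 20 and 26 after discharge (5.1). For a family that attends no home visit, with none rescheduled:

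| NICCU sessions missed | Section 8 (4th miss) | Section 4.4 (6th miss) |
|---|---|---|
| 0 | week 8 | week 15 |
| 1 | week 5 | week 11 |
| 2 | week 3 | week 8 |

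Age at discharge is an assumption: 72 hours of cooling from birth plus the 3 to 7 days quoted in the Study Rationale gives 6 to 10 days (0.9 to 1.4 weeks). Week 8 is then 8.9–9.4 weeks of age, week 11 is 11.9–12.4, and week 15 is 15.9–16.4. A2 at 3 months is about 13 weeks. Week 8 precedes A2 for any discharge before 13 − 8 = 5 weeks of age; week 11 does so for discharge before 13 − 11 = 2 weeks. (The table in 6.1 places six home sessions before A2; on these weeks and ages only five fall before it.)

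**4. Instability and 10-day gaps, reading days as calendar days**

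The log samples one day a week for 26 weeks, and H2b needs 0.8 × 26 = 20.8, so 21 days. A gap of g days touches at most ceil((g − 1)/7) + 1 weeks:

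- g = 3 or 4: 2 weeks, leaving 24/26 = 92%;
- g = 10 or 11: 3 weeks, leaving 23/26 = 88%.

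The closest home visits are 14 days apart, so after discharge such a gap covers at most one visit and 9 of 10 remains possible. These rules can remove a dyad that could still meet H2a and H2b.

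**5. How many dyads could be treated differently**

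The two missed-visit rules disagree for dyads missing 4 or 5 visits, and for those missing 6 or more while in contact. Expected number among 20 = 20 × P(4 or 5 missed of 10) as the lower end (none of those missing 6 or more in contact) and 20 × P(4 or more missed) as the upper end (all in contact). Attendance and the within-family correlation (ICC) are assumptions; the model is binomial at ICC 0 and beta-binomial otherwise.

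| Attendance | ICC 0 | ICC 0.1 | ICC 0.3 |
|---|---|---|---|
| 90% | 0.25–0.26 | 0.97–1.15 | 1.16–2.04 |
| 80% | 2.29–2.42 | 2.89–3.76 | 2.33–4.60 |
| 70% | 6.06–7.01 | 5.01–7.42 | 3.29–7.43 |

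**6. Effect on H3a**

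1/20 = 5 points per dyad withdrawn before A3, if all 20 enrolled dyads are the denominator and that dyad would otherwise have completed its assessments. Two such dyads cap H3a at 90%, four at 80%.

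**7. Referred infants**

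They omit the 2 NICCU sessions, so 8 of 10 visits becomes 8 of 8. Eighty per cent of 8 is 6.4, so 7 of 8 would be the equivalent.

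**The case against.** The strongest reply is that section 8 leaves the decision to judgement. Its list says what the investigator may do, its first sentence makes continued assessment the default, and after a missed visit staff must try to reschedule within a week and find out whether the family wishes to or should continue. Telehealth is allowed. Reasons for withdrawal are recorded. This is a single-arm pilot with descriptive proportions, so no comparison between arms can be biased, and H3a has no pass mark for the cohort. A section 8 limit that matches the 5.4 cut-off is also coherent in itself.

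Most of this stands, and it rules out three stronger readings:

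- A reader might infer that section 8 forces H3a failures. It does not, because missed-visit withdrawal is discretionary.
- A reader might infer that only section 8 can cost A2. Section 4.4 is also a study-level rule, and it can cost A2 when NICCU sessions are missed.
- A reader might infer that every withdrawal takes 5 points off H3a. Section 9.5 fixes no denominator, and a family that has stopped attending might have missed A2 and A3 anyway.

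The reply does not settle which limit applies. Rescheduling and contact attempts mainly serve families who are out of touch. For a family that is reachable but not doing SMI, continued assessment is a default that the same section lets the investigator set aside.

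**Conclusion.** The concern holds in this form: the two sections conflict on study-withdrawal limits, and both allow missed SMI to end assessment. The conflict is plain in the text and needs no assumption. The week-8 and week-15 timings rest on the 5.1 schedule with no visit made up; their position relative to A2 also rests on age at discharge. The number of dyads affected, from about 0.3 to 7.4 of 20, depends entirely on assumed attendance, correlation and contact, and counts dyads who could be treated differently, not dyads who will be. The point about brief gaps assumes calendar days, which is the likelier reading because more than 10 session days cannot occur with 10 planned sessions. This should be fixed. It does not threaten the trial's validity, but it can remove primary-endpoint and parent-stress data from the families about whom a feasibility study most needs to learn.

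**What to change.** 1. In 4.4 and 8, make missed visits, gaps in SMI and medical instability reasons to pause or stop SMI only. Continue A2 and A3 when the infant is medically able, unless consent is withdrawn or the family cannot be reached.
2. Use one missed-visit limit and one instability limit, worded identically in both sections, with days defined and the lost-to-follow-up count aligned. The clinical team should choose the values.
3. In 9.5, keep withdrawn dyads who started SMI in the H2a, H2b and H3a denominators as non-completers, and report how many were withdrawn by the investigator.
4. For referred infants with 8 planned sessions, apply H2a as at least 80% of planned sessions (7 of 8).

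The cost is rewording three sections and the effort of assessing families who have stopped SMI. Reported H2 and H3 proportions may be lower than if withdrawn dyads were left out.
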